Clinical Study ARRAY-382-201

**A Phase 1b/2 Study of ARRY-382 in Combination with Pembrolizumab,
a Programmed Cell Death Receptor 1 (PD-1) Antibody, for the Treatment of
Patients with Advanced Solid Tumors**

Protocol Version 1: 12 April 2016

Protocol Version 2: 19 December 2016

Protocol Version 3: 16 March 2018

Protocol Version 4: 24 July 2018

Array BioPharma Inc.

[name]
[name]
[contact]
[contact]

CONFIDENTIAL INFORMATION

This document contains trade secrets and other confidential and proprietary information belonging to Array BioPharma Inc. Except as otherwise agreed to in writing, by accepting or reviewing this document you agree to hold this information in confidence and not to disclose it to others (except where required by applicable law) or to use it for unauthorized purposes. In the event of any actual or suspected breach of this obligation, Array BioPharma Inc. should be promptly notified.

CCI

PROTOCOL SYNOPSIS

Title	A Phase 1b/2 Study of ARRY-382 in Combination with Pembrolizumab, a Programmed Cell Death Receptor 1 (PD-1) Antibody, for the Treatment of Patients with Advanced Solid Tumors
Protocol Number	ARRAY-382-201
Phase	Phase 1b/2
Study Center(s)	Approximately 30 centers
Objectives and Endpoints	
Phase 1b/Part A
 
Primary objective:
 
• To determine the maximum tolerated dose (MTD) and/or recommended Phase 2 dose (RP2D) of ARRY-382 in combination with pembrolizumab in patients with selected solid tumors 
Primary endpoint:
 
• Incidence of dose-limiting toxicities (DLTs), as a function of the dose of ARRY-382 when administered in combination with pembrolizumab 
Secondary objectives:
 
• To describe the preliminary antitumor activity of the combination based on the Response Criteria In Solid Tumors, version 1.1 (RECIST v1.1)• To describe the preliminary antitumor activity of the combination based on immune-related response criteria (irRC)• To characterize the safety and tolerability of the combination, including acute and chronic toxicities• To evaluate the pharmacokinetics (PK) of ARRY-382 in combination with pembrolizumab 
Secondary endpoints:
 
• Objective response rate (ORR), as determined by the Investigator

	
• Duration of response (DOR), as determined by the Investigator• Progression-free survival (PFS), as determined by the Investigator• Overall survival (OS)• Immune-related response rate (irRR), as determined by the Investigator• Immune-related progression-free survival (irPFS), as determined by the Investigator• Type, frequency, and severity of adverse events (AEs), using the National Cancer Institute (NCI) Common Terminology Criteria for Adverse Events (CTCAE)• Serious adverse events (SAEs), using the NCI CTCAE• Clinical laboratory values• Vital signs• Plasma concentration-time profiles• PK parameters (e.g., area under the plasma concentration-time curve over the dosing interval [AUC_{τ}], maximum observed plasma concentration [C_{max}], time of maximum observed plasma concentration [T_{max}], plasma concentration measured just before the next dose of study drug [C_{trough}], accumulation ratio, and metabolite-to-parent ratio) for ARRY-382 and its metabolites, AR00469099, AR00469100, and AR00470870 
CCI [REDACTED]
 
■ [REDACTED]■ [REDACTED]■ [REDACTED]
--	---

	
CCI [REDACTED]
 
[REDACTED][REDACTED][REDACTED][REDACTED][REDACTED] 
Phase 2: PD-1 or PD-L1 Inhibitor Refractory
 
Primary objective:
 
To estimate the efficacy of ARRY-382 in combination with pembrolizumab in patients with advanced solid tumors following progression on prior PD-1/PD-L1 inhibitor therapy 
Primary endpoint:
 
ORR, per RECIST v 1.1, as determined by the Investigator 
Secondary objectives:
 
To further estimate the efficacy of the combinationTo characterize the safety and tolerability of the combination, including acute and chronic toxicitiesTo evaluate the PK of ARRY-382 in combination with pembrolizumab 
Secondary endpoints:
 
DOR, per RECIST v1.1, as determined by the InvestigatorPFS, per RECIST v1.1, as determined by the Investigator
--	---

	
C C I I
 
[REDACTED]
 
[REDACTED]
 
Phase 2: Platinum-resistant Ovarian Cancer
 
Primary objective:
 
• To estimate the efficacy of ARRY-382 in combination with pembrolizumab in patients with microsatellite stable (MSS)/mismatch repair (MMR)-proficient platinum-resistant ovarian cancer (prOVCA) 
Primary endpoint:
 
• ORR, per RECIST v1.1, as determined by the Investigator 
Secondary objectives:
 
• To further estimate the efficacy of the combination in patients with MSS/MMR-proficient prOVCA• To estimate the efficacy of the combination, as assessed by changes in tumor markers from baseline• To characterize the safety and tolerability of the combination, including acute and chronic toxicities• To evaluate the PK of ARRY-382 in combination with pembrolizumab 
Secondary endpoints:
 
• DOR, per RECIST v1.1, as determined by the Investigator• PFS, per RECIST v1.1, as determined by the Investigator• irRR, per irRC, as determined by the Investigator• irPFS, per irRC, as determined by the Investigator• OS• Changes from baseline in relevant tumor markers• Type, frequency, and severity of AEs, using the NCI CTCAE• SAEs, using the NCI CTCAE• Clinical laboratory values• Vital signs• Plasma concentration-time profiles
--	---

	
• PK parameters (e.g., AUC_{τ}, C_{max}, T_{max}, C_{trough}, accumulation ratio, and metabolite-to-parent ratio) for ARRY-382 and its metabolites, AR00469099, AR00469100, and AR00470870 
CCI [REDACTED]
 
█ [REDACTED]█ [REDACTED]█ [REDACTED]█ [REDACTED] 
CCI [REDACTED]
 
█ [REDACTED]█ [REDACTED]█ [REDACTED]█ [REDACTED]█ [REDACTED]█ [REDACTED]█ [REDACTED]█ [REDACTED] 
Phase 2: Pancreatic Ductal Adenocarcinoma
 
Primary objective:
 
• To estimate the efficacy of ARRY-382 in combination with pembrolizumab in patients with MSS/MMR-proficient pancreatic ductal adenocarcinoma (PDA)
--	---

	
Primary endpoint:
 
• ORR, per RECIST v 1.1, as determined by the Investigator 
Secondary objectives:
 
• To further estimate the efficacy of the combination in patients with MSS/MMR-proficient PDA• To characterize the safety and tolerability of the combination, including acute and chronic toxicities• To evaluate the PK of ARRY-382 in combination with pembrolizumab 
Secondary endpoints:
 
• DOR, per RECIST v1.1, as determined by the Investigator• PFS, per RECIST v1.1, as determined by the Investigator• irRR, per irRC, as determined by the Investigator• irPFS, per irRC, as determined by the Investigator• OS• Type, frequency, and severity of AEs, using the NCI CTCAE• SAEs, using the NCI CTCAE• Clinical laboratory values• Vital signs• Plasma concentration-time profiles• PK parameters (e.g., AUC_{τ}, C_{max}, T_{max}, C_{trough}, accumulation ratio, and metabolite-to-parent ratio) for ARRY-382 and its metabolites, AR00469099, AR00469100, and AR00470870 
CCI [REDACTED]
 
• [REDACTED]• [REDACTED]• [REDACTED]
--	---

	
C C I
 
[Redacted text]

Design	
This is an open-label, multicenter Phase 1b/2 study to determine the MTD and/or RP2D of ARRY-382 in combination with pembrolizumab in adult patients with selected advanced solid tumors (Part A/Phase 1b); and to estimate the efficacy of the combination in patients with advanced solid tumors that have progressed on prior PD-1/PD-L1 inhibitors, in patients with prOVCA and in patients with PDA (Phase 2).
 
Part A (Phase 1b) includes a dose-escalation component with 2 planned dose cohorts (200 mg once daily [QD] and 400 mg QD). Oral doses of ARRY-382 will be administered QD in combination with pembrolizumab 2 mg/kg intravenously (iv) every 3 weeks (Q3W). Patients in Cohort 1 will be enrolled on a rolling basis up to 6 evaluable patients or until DLTs are observed in more than 1 patient during Cycle 1. If fewer than 2 of 6 patients experience a DLT during Cycle 1, patients in Cohort 2 will receive ARRY-382 400 mg QD. If 2 or more patients in Cohort 1 experience DLTs during Cycle 1, the dosage of ARRY-382 in Cohort 2 will be 100 mg

	
QD. If a Grade 3 immune-related adverse event (irAE) (first occurrence) is reported in a given cohort, enrollment in that cohort will continue at the same dose until the toxicity is evaluated. If a second Grade 3 irAE is reported or a first Grade 3 irAE is reported in addition to a previous DLT in a given cohort, enrollment of new patients in that cohort will be stopped until the Grade 3 irAE is evaluated. If the event is not a DLT (as determined by the Investigators in consultation with the Sponsor), then enrollment may be resumed, or the cohort may be expanded to include up to 9 patients. If the Grade 3 irAE is deemed a DLT, the MTD has been achieved and additional patients will be enrolled at the previous dose level or at an intermediate dose level.
 
Intermediate doses and doses higher than 400 mg QD may also be considered upon review of the safety and PK results from the planned dose cohorts. In the absence of identification of an MTD, a dose of 400 mg or lower may be selected as the RP2D as long as the DLT rate is < 33% (e.g., fewer than 2 of 6 patients experience a DLT).
 
Part A has been completed and the MTD/RP2D of ARRY-382 was determined to be 300 mg QD in combination with pembrolizumab.
 
Phase 2 will consist of 3 separate cohorts of patients. The Phase 2 PD-1/PD-L1 Inhibitor Refractory cohort will consist of patients with advanced solid tumors who progressed on a PD-1/PD-L1 inhibitor-containing regimen as their most recent prior line of therapy are who are naïve to prior CSF-1R or CSF-1 inhibitors. The Phase 2 prOVCA and PDA cohorts will consist of patients with prOVCA and patients with PDA, respectively, who have had at least one prior line of therapy and who are naïve to prior checkpoint inhibitor (CPI) therapy and to prior CSF-1R or CSF-1 inhibitors.
 
In Phase 2, at baseline, submission of archived tumor tissue from the most recent sample collection available or a fresh biopsy will be required.
 
All patients in Phase 2 will receive ARRY-382 at 300 mg QD, the MTD/RP2D determined during Part A, in combination with pembrolizumab 200 mg iv Q3W.
 
Efficacy assessments include determination of objective response using RECIST v1.1. For patients who have initial evidence of radiological progressive disease (PD) by RECIST v1.1, it will be at the discretion of the Investigator to keep a patient on study treatment or to stop study treatment until repeat imaging is performed approximately 4 weeks later in order to confirm PD per irRC. Patients with confirmed irPD should discontinue treatment. Patients

--	--

	
with a declining Eastern Cooperative Oncology Group performance status (ECOG PS), deteriorating clinical symptoms or rapid progression of disease/progression at critical anatomical sites (i.e., central nervous system [CNS]) should be considered for treatment discontinuation based on clinical judgment.
 
CCI
  
Pharmacokinetic assessments include determination of plasma concentrations of ARRY-382 and its metabolites.
 
Safety assessments include monitoring of AEs, clinical laboratory tests (hematology, coagulation, clinical chemistry, thyroid panel, and urinalysis), physical examinations, vital signs, and electrocardiograms (ECGs). ECOG PS will also be assessed.

Treatment Regimens	
ARRY-382: Patients in Part A (Phase 1b dose escalation) will receive oral doses of single-agent ARRY-382 capsules in combination with pembrolizumab; planned dose levels of ARRY-382 are 200 mg QD and 400 mg QD.
 
Patients in Phase 2 will receive oral doses of ARRY-382 capsules at 300 mg QD, the MTD/RP2D determined during Part A, in combination with pembrolizumab.
 
Pembrolizumab: Patients in Part A will receive 2 mg/kg pembrolizumab administered by study site personnel as an iv infusion over 30 minutes Q3W. Patients in Phase 2 will receive 200 mg pembrolizumab administered by study site personnel as an iv infusion over 30 minutes (within -5 to +10 minutes) Q3W.
 
In all phases of the study, patients will continue to receive ARRY-382 in combination with pembrolizumab until disease progression as determined by the Investigator, withdrawal of consent, initiation of subsequent anticancer therapy, the patient is lost to follow-up, or death, whichever occurs first.

Study Population	
Overall, approximately 90 patients are planned for enrollment.
 
Part A (Phase 1b) will consist of approximately 18 patients with advanced/metastatic melanoma, PD-L1–positive NSCLC, ovarian cancer, triple-negative breast cancer, head and neck squamous cell

	
carcinoma (HNSCC), bladder cancer, metastatic colorectal cancer (CRC), PDA, or gastric cancer. Patients who had prior treatment with an immune CPI (e.g., programmed cell death receptor 1 [PD-1], PD-L1, or cytotoxic T-lymphocyte antigen 4 [CTLA-4] inhibitor) will be excluded. Prior treatment with ipilimumab administered as adjuvant therapy in patients with melanoma is allowed. Prior treatment with a CSF-1R or CSF-1 (or macrophage colony-stimulating factor [MCSF]) inhibitor is allowed.
 
The Phase 2 PD-1/PD-L1 Inhibitor Refractory cohort will consist of up to 20 patients with advanced solid tumors who progressed on a PD-1/PD-L1 inhibitor-containing regimen as their most recent prior line of therapy. If clinical activity is observed, enrollment may be focused to include up to 10 additional patients with particular tumor histologies of interest.
 
The Phase 2 prOVCA cohort will consist of approximately 23 patients with prOVCA who are naïve to prior CPI therapy. The Phase 2 PDA cohort will consist of approximately 29 patients with PDA who have had at least one prior therapy who are naïve to prior CPI therapy.

Duration of Study Participation
	
Each phase of the study consists of a 28-day screening period; 21-day treatment cycles with the combination of ARRY-382 and pembrolizumab until disease progression as determined by the Investigator, unacceptable toxicity, withdrawal of consent, or death (or other discontinuation criteria are met); and a 30-day safety follow-up period.
 
Patients will be monitored for OS until 1 year after the date of the last patient’s first visit.

Statistical Considerations
	
For Part A, the sample size of approximately 18 evaluable patients (i.e., 6 to 9 patients in each dose cohort) is standard for purposes of determining the MTD and RP2D. Patients will be considered evaluable if they complete Cycle 1 or discontinue treatment due to DLT during Cycle 1.
 
For the Phase 2 PD-1/PD-L1 Inhibitor Refractory cohort, the sample size of up to 20 patients will be evaluated for initial evidence of activity in this PD-1/PD-L1 inhibitor-refractory population.
 
For the Phase 2 prOVCA cohort, a Simon’s 2-stage optimal design will be used in the MSS/MMR-proficient prOVCA population. The null hypothesis of the true response rate is 15%, versus alternative of 35%. Accrual of patients in Stage 1 will continue until 9 evaluable

	
MSS/MMR-proficient patients have been enrolled, with evaluable defined as having received at least one dose of study drug. The analysis for Stage 1 will not occur until all evaluable patients in Stage 1 have had the opportunity to have at least 2 post-baseline tumor assessments (or have discontinued tumor assessments beforehand). If there are less than 2 responders in these 9 patients, enrollment into this cohort of the study will be stopped. Otherwise, 14 additional patients will be accrued during Stage 2, for a total of 23 patients enrolled in this cohort. The null hypothesis will be rejected if 6 or more responses are observed in 23 patients. With this sample size, the actual Type I error is 9.9%, and the power is 80%. If the null hypothesis is true, the expected sample size is 15 patients, and the probability of stopping enrollment into this cohort of the study early is 60%. Patients who are MSI-H/mismatch repair-deficient (dMMR) will not be included in the Simon's 2-stage analyses and the study will ensure that the sample size requirements are met by enrolling the required number of MSS/MMR-proficient prOVCA patients.
 
For the Phase 2 PDA cohort, a Simon's 2-stage optimal design will be used in the MSS/MMR-proficient PDA population. The null hypothesis of the true response rate is 4%, versus alternative of 15%. Accrual of patients in Stage 1 will continue until 15 evaluable MSS/MMR-proficient patients have been enrolled, with evaluable defined as having received at least one dose of study drug. The analysis for Stage 1 will not occur until all evaluable patients in Stage 1 have had the opportunity to have at least 2 post-baseline tumor assessments (or have discontinued tumor assessments beforehand). If there are no responders in these 15 patients, enrollment into this cohort of the study will be stopped. Otherwise, 14 additional MSS/MMR-proficient patients will be accrued during Stage 2, for a total of 29 patients enrolled in this cohort. The null hypothesis will be rejected if 3 or more responses are observed in 29 MSS/MMR-proficient patients. With this sample size, the actual Type I error is 9.9%, and the power is 80%. If the null hypothesis is true, the expected sample size is 21 patients, and the probability of stopping enrollment into this cohort of the study early is 54%. PDA patients who are MSI-H/dMMR will not be included in the Simon's 2-stage analyses and the study will ensure that the sample size requirements are met by enrolling the required number of MSS/MMR-proficient PDA patients.
 
Objective response rate and 95% confidence intervals (CIs) will be reported. For time-to-event variables (i.e., DOR, PFS, OS), the survival distribution functions will be estimated using the Kaplan-

--	--

	
Meier method.
 
Data for tumor genomic alterations, gene expression profiles ^{CCI} [REDACTED] will be presented in tabular and/or graphical format and summarized descriptively. Absolute data, change from baseline and/or percentage change from baseline will be summarized by dose level, as appropriate.
 
Plasma concentrations of ARRY-382 and metabolites, AR00469099, AR00469100, and AR00470870, will be determined using a validated bioanalytical method. Standard noncompartmental and/or compartmental PK parameters (e.g., C_{max} and area under the curve [AUC]) will be estimated for each patient. Descriptive statistics of PK parameters will be reported for each cohort and summarized. Dose proportionality, metabolite-to-parent ratio and drug accumulation will be assessed as appropriate. Other model-dependent PK analysis approaches (e.g., maximum a posteriori Bayesian parameter estimation, nonlinear mixed effects modeling) may also be applied to the data as appropriate. ^{CCI} [REDACTED]
 
^{CCI} [REDACTED]
 
^{CCI} [REDACTED] Parametric PK ^{CCI} [REDACTED] models may be assessed for suitability and used in describing PK ^{CCI} [REDACTED] results. Results may be summarized graphically or with summary statistics.
 
Safety data will be presented in tabular and/or graphical format and summarized descriptively by treatment group and study day, where appropriate. Adverse events will be coded using the Medical Dictionary for Regulatory Activities (MedDRA[®]). Incidence tables will be presented for DLTs, all AEs by maximum severity, SAEs, AEs assessed as related to study drug and AEs resulting in discontinuation of study drug. Dose-limiting toxicities will be listed for Part A. Changes in ECG and laboratory measurements will be summarized. Listings of all safety data sorted by treatment group, patient and assessment date will be provided.

Sponsor	Array BioPharma Inc.

TABLE OF CONTENTS

1.0	INVESTIGATORS AND STUDY ADMINISTRATIVE STRUCTURE	48
2.0	INTRODUCTION	49
2.1	Background Therapeutic Information	49
2.1.1	PD-1 and PD-L1 Inhibitor Resistance	50
2.1.2	Malignant Melanoma	50
2.1.3	Non-Small Cell Lung Carcinoma	51
2.1.4	Ovarian Cancer	52
2.1.5	Pancreatic Cancer	52
2.2	Investigational Medicinal Product	53
2.2.1	Nonclinical Studies with ARRY-382	53
2.2.2	Clinical Experience with ARRY-382 (Clinical Study ARRAY-382-101)	55
2.3	Rationale for the Current Study	59
2.3.1	Phase 1b (Part A)	59
2.3.2	Phase 2	60
2.4	Dose Selection	61

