2.1.4 Ovarian Cancer

Ovarian cancer ranks fifth in cancer deaths among women, accounting for more deaths than any other cancer of the female reproductive system ([American Cancer Society 2018](#)). Despite surgery and platinum- and taxane-based chemotherapies, greater than 70% of patients with advanced ovarian cancer who achieve remission ultimately experience relapse. Because there are few effective treatments for these patients the development of new treatment strategies is urgently required ([Hamanishi et al 2015](#)). In platinum-resistant ovarian cancer (prOVCA), current standard-of-care includes single-agent chemotherapeutic agents which have ORRs of 20% to 25% and median PFS of approximately 3 months ([Herzog and Monk 2017](#)). In a recent Phase 3 study, bevacizumab added to chemotherapy resulted in ORR of 27% and PFS of 6.7 months ([Pujade-Lorraine et al 2014](#)).

In recent years, there has been some progress made with achieving response with immunotherapy. In the KEYNOTE-028 trial of pembrolizumab in patients with advanced solid tumors, data were reviewed for the 26 patients enrolled with PD-L1-positive ovarian cancer. In this patient population, the ORR was 11.5% with 1 complete response (CR) and 2 partial responses (PRs) achieved. Median PFS and overall survival (OS) were 1.9 months and 13.1 months, respectively ([Varga et al 2017](#)). Results are pending for a follow-up Phase 2 study (KEYNOTE-100; NCT02674061) in women with advanced ovarian cancer ([ClinicalTrials.gov NCT02674061](#)).

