### 4.2 Secondary Endpoints

#### Phase 1b/Part A:

- ORR, as determined by the Investigator
- Duration of response (DOR), as determined by the Investigator
- Progression-free survival (PFS), as determined by the Investigator
- Overall survival (OS)
- Immune-related response (irRR), as determined by the Investigator
- Immune-related progression-free survival (irPFS), as determined by the Investigator
- Type, frequency, and severity of AEs, using the National Cancer Institute (NCI) Common Terminology Criteria for Adverse Events (CTCAE)
- Serious adverse events (SAEs), using the NCI CTCAE
- Clinical laboratory values
- Vital signs
- Plasma concentration-time profiles
- PK parameters (e.g., area under the plasma concentration-time curve over the dosing interval  $[AUC_T]$ , maximum observed plasma concentration  $[C_{max}]$ , time of maximum observed plasma concentration  $[T_{max}]$ , plasma concentration measured just before the

next dose of study drug [ $C_{\text{trough}}$ ], accumulation ratio, and metabolite- to-parent ratio) for ARRY-382 and its metabolites, AR00469099, AR00469100, and AR00470870

Phase 2: PD-1 or PD-L1 Inhibitor Refractory:

- DOR, per RECIST v1.1, as determined by the Investigator
- PFS, per RECIST v1.1, as determined by the Investigator
- irRR, per irRC, as determined by the Investigator
- irPFS, per irRC, as determined by the Investigator
- OS
- Type, frequency, and severity of AEs, using the NCI CTCAE
- SAEs, using the NCI CTCAE
- Clinical laboratory values
- Vital signs
- Plasma concentration-time profiles
- PK parameters (e.g.,  $AUC_{\tau}$ ,  $C_{\text{max}}$ ,  $T_{\text{max}}$ ,  $C_{\text{trough}}$ , accumulation ratio, and metabolite-to-parent ratio) for ARRY-382 and its metabolites, AR00469099, AR00469100, and AR00470870

Phase 2: Platinum-resistant Ovarian Cancer:

- DOR, per RECIST v1.1, as determined by the Investigator
- PFS, per RECIST v1.1, as determined by the Investigator
- irRR, per irRC, as determined by the Investigator
- irPFS, per irRC, as determined by the Investigator
- OS
- Changes from baseline in relevant tumor markers
- Type, frequency, and severity of AEs, using the NCI CTCAE
- SAEs, using the NCI CTCAE
- Clinical laboratory values
- Vital signs
- Plasma concentration-time profiles

- PK parameters (e.g.,  $AUC_{\tau}$ ,  $C_{max}$ ,  $T_{max}$ ,  $C_{trough}$ , accumulation ratio, and metabolite-to-parent ratio) for ARRY-382 and its metabolites, AR00469099, AR00469100 and AR00470870

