## 7.6 Safety Analysis

All safety analyses will be performed using the appropriate data for all patients in the SS unless otherwise stated.

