### 7.6.4 Adverse Events

AEs and serious adverse events (SAEs) will be coded by PT and SOC using the latest available MedDRA version.

The severity of an AE will be assessed by the investigator using the NCI CTCAE, Version 4.03. For patients with more than 1 AE within a SOC or PT, only the highest grade will be included in by-severity summaries.

The investigator will also assess whether the AE is suspected to be related to study drug (i.e., a treatment-related AE). For patients with more than 1 AE within a SOC or PT, the highest level of relationship (related is higher than not related) will be included in the by-relationship summaries.

For summaries by SOC and PT, each patient will be counted at most once per SOC and at most once per PT. For summaries by PT, each patient will be counted at most once per PT.

Treatment-emergent AEs (TEAEs) will be defined as:

- Any new event that starts after administration of study drug and  $\leq 30$  days after treatment discontinuation.
- Any event that was ongoing when treatment with study drug started and the severity/grade after treatment was higher than the Baseline value (fluctuations below the Baseline severity/grade are not considered as treatment emergent).
- Any new event that starts  $> 30$  days after treatment discontinuation and is assessed by the Investigator as related to study treatment.

Every effort should be made to obtain start dates for adverse events (AEs). If an AE is missing the start date, and the timing of the start date relative to treatment start is not known, it should be considered as treatment emergent for reporting and analysis purposes.

Unless otherwise stated, only TEAEs will be presented in summary tables. However, all AEs will be presented in listings.

Overall summary of safety table will include numbers and percentages of the following:

- Patients who died on study or within 30 days of last treatment
- Patients with at least 1 TEAE regardless of causality
- Patients with at least 1 treatment related TEAE
- Patients with treatment related TEAEs by worst severity
- Patients with at least 1 treatment-emergent SAE (TESAE)
- Patients with at least 1 treatment-related TESAE
- Patients who discontinued study drug due to a TEAE regardless of causality
- Patients who discontinued study drug due to a treatment-related TEAE
- Patients with a dose reduction due to a TEAE
- Patients with a dose interruption due to a TEAE

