All TEAE summaries will be displayed (frequency counts and percentages) alphabetically by system organ class (SOC) and preferred term (PT) by descending frequency within SOC, if not otherwise noted. Individual summary tables showing the incidence of patients with the following subsets of TEAEs will be generated:

- TEAEs, regardless of causality, by SOC, PT and maximum severity
- TEAEs, regardless of causality, by SOC and PT
- TEAEs, regardless of causality, by PT
- Treatment-related TEAEs with suspected relationship to ARRY-382 by SOC, PT and maximum severity
- Treatment-related TEAEs with suspected relationship to pembrolizumab by SOC, PT and maximum severity
- Treatment-related TEAEs with suspected relationship to ARRY-382 by PT
- Treatment-related TEAEs with suspected relationship to pembrolizumab by PT
- TESAEs, regardless of causality, by SOC, PT and maximum severity
- TESAEs, regardless of causality, by SOC and PT
- TESAEs, regardless of causality, by PT
- TESAEs with suspected relationship to ARRY-382 by SOC, PT and maximum severity
- TESAEs with suspected relationship to pembrolizumab by SOC, PT and maximum severity

- TEAEs, regardless of causality, that led to discontinuation of study drug, by SOC and PT
- Treatment-related TEAEs with suspected relationship to ARRY-382 leading to study drug discontinuation by SOC and PT
- Treatment-related TEAEs with suspected relationship to pembrolizumab leading to study drug discontinuation by SOC and PT
- TEAEs that led to dose reduction in ARRY-382 by SOC and PT
- TEAEs that led to dose interruption /delay of ARRY-382 by SOC and PT
- TEAEs that led to dose interruption /delay of pembrolizumab by SOC and PT
- Non-serious TEAEs, regardless of causality, by SOC and PT
- TEAEs that resulted in death on study or within 30 days of last study treatment by SOC and PT

Separate listings for AEs, serious AEs (SAEs), AEs requiring dose interruption, AEs leading to any study drug discontinuation, and death recorded during the study will be provided.

All AEs and their attributes will be presented in data listings sorted by patient identifier, AE and date of onset of the AE.

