- If fasting status is known and fasting did not occur, and the result falls within the ranges for hyperglycemia grades 1 or 2, grade should be set to 0.

The following laboratory parameters will be summarized by normal range:

- Hematology:  
Hematocrit, RBC, Monocytes (absolute), Eosinophils (absolute), Basophils (absolute).
- Chemistry:  
Bicarbonate (CO2), BUN or urea, Chloride, Glucose (non-fasting), LDH, Total protein, Direct bilirubin.
- Urinalysis:  
Specific gravity, Glucose, Ketones, Blood, Nitrite, Leukocytes.
- Thyroid panel:  
Thyroid-Stimulating Hormone (TSH)  
Triiodothyronine (T3), free  
Thyroxine (T4), free

The Corrected Calcium will be derived from Calcium and Albumin results as per the following formula:

$$\text{Corrected calcium (mmol/L)} = [4 * \text{calcium (mmol/L)} - 0.8 * (0.1 * \text{albumin (g/L)} - 4)] / 4$$

The normal range of the Calcium will be used as normal range for Corrected Calcium.

The following summaries will be produced for the hematology, coagulation, clinical chemistry, thyroid panel and urinalysis laboratory data (by laboratory parameter):

- Shift tables using CTCAE grades to compare baseline to the worst post-baseline value for laboratory parameters with CTCAE grades. For the laboratory parameters like blood glucose where patients can be graded for decreased or increased values, the worst post-baseline CTCAE grade will be presented for decrease and increase separately (e.g. hyperglycemia and hypoglycemia). In the description of worst grade increase, a decrease of a grade  $\geq 1$  will be described as grade 0. The reciprocal will be applied for grade decrease categorization.
- Shift tables using low, normal, high (as well as low and high combined) classifications to compare baseline to the worst post-baseline value for laboratory parameters where CTCAE grades are not defined.
- The following listings will be produced for the laboratory data for all laboratory parameters where CTCAE grades are defined:
  - Listing of all laboratory data with values flagged to show the corresponding CTCAE grades and the classifications relative to the laboratory reference ranges.
  - Listing of patients with laboratory abnormalities of CTCAE grade 3 or 4.

Serology test results will be summarized.

All lab test results will be presented in listings sorted by patient identifier, lab test, and date/time of collection. Values outside laboratory normal ranges will be flagged where appropriate.

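### The safety objective covers acute and chronic toxicity, but the planned adverse event tables ignore onset time and number at risk, so they understate late-onset risk; a few onset-interval tables would close the gap.

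*Protocol*

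**What the plan says.** The objective "To characterize the safety and tolerability of the combination, including acute and chronic toxicities" stands in the Protocol Synopsis and in Protocol Tables 2 to 5 for Part A and each Phase 2 cohort. SAP 2.2 repeats it. Neither document defines acute or chronic. The adverse event endpoint paired with it is "Type, frequency, and severity of AEs, using the NCI CTCAE" (SAP 4.2), which has no timing component.

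Protocol 11.1.6 says safety data will be "summarized descriptively by treatment group and study day, where appropriate". The same paragraph asks for incidence tables of adverse events by maximum severity, serious events, related events and events leading to discontinuation.

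SAP 7.6 sets the population: "All safety analyses will be performed using the appropriate data for all patients in the SS unless otherwise stated". SAP 5.4 admits anyone with one partial dose of either drug. SAP 7.6.4 defines the treatment-emergent window as running to 30 days after discontinuation, plus later events judged related. For summaries by system organ class (SOC) and preferred term (PT), "each patient will be counted at most once per SOC and at most once per PT". It then lists 20 individual tables, of which the first is "TEAEs, regardless of causality, by SOC, PT and maximum severity". None is split by cycle, study day or onset period, and none gives time to onset, duration or an exposure-adjusted rate. Onset date is used to sort listings. Exposure is summarised separately in SAP 7.6.1. Graded laboratory results go into "Shift tables using CTCAE grades to compare baseline to the worst post-baseline value" (SAP 7.6.5).

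**The concern.** Treatment is open-ended, so exposure will vary widely. Protocol 2.3.2 reports a Part A responder with pancreatic cancer who stayed on study for more than 17 cycles (17 × 21 = 357 days). For pembrolizumab alone in PD-L1-positive ovarian cancer, Protocol 2.1.4 says "Median PFS and overall survival (OS) were 1.9 months and 13.1 months" respectively.

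A patient who leaves at week 5 cannot contribute a week-20 event, yet remains in the denominator. For toxicity that starts early this matters little. For toxicity that needs longer dosing, the crude percentage falls below the risk faced by a patient who stays on treatment. The sponsor's own Study 101 had both kinds of timing: the two treatment-related discontinuations at 200 mg were for raised ALT at Day 21 and petechiae at Day 70 (Protocol 2.2.2.1).

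At stake is whether the planned summaries tell a reader anything about the later half of the stated objective.

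**Working it through.** The plan states no figure for late toxicity or for patients still at risk, so there is nothing of its own to reproduce. The check sizes the dilution under stated assumptions.

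**Inputs**
- Phase 2 cohort sizes: about 20 refractory, 23 ovarian, 29 pancreatic (SAP 3.2); total 20 + 23 + 29 = 72.
- Assumed time on treatment: exponential with median m = 1.9, 3.0 or 6.7 months. These are PFS figures cited in Protocol 2.1.4 for ovarian cancer (pembrolizumab alone, single-agent chemotherapy, chemotherapy plus bevacizumab). They are stand-ins, not time-on-treatment data.
- 1 month = 30.4375 days (SAP 7.1.7).
- Landmark: week 12 = 84 days = four 21-day cycles, so later onset means Cycle 5 onward when there are no delays.

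**Formulas**
- Share still on treatment at week 12: S = 2^(−(84/30.4375)/m) = 2^(−2.760/m).
- Share on treatment or within 30 days of last dose: W = 2^(−((84 − 30)/30.4375)/m) = 2^(−1.774/m). This matches the treatment-emergent window, apart from the later related events.
- Crude percentage = risk among those at risk at week 12 × share. The understatement factor is therefore 1/share, whatever the risk.

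**Results at week 12**

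| Median (months) | S | 1/S | W | 1/W |
|---|---|---|---|---|
| 1.9 | 0.365 | 2.7 | 0.524 | 1.9 |
| 3.0 | 0.529 | 1.9 | 0.664 | 1.5 |
| 6.7 | 0.752 | 1.3 | 0.832 | 1.2 |

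A 20% risk among those at risk at week 12 would be tabulated, with the 30-day tail at risk, as 20% × W = 10.5%, 13.3% or 16.6%. With only patients on treatment counted, it would be 20% × S = 7.3%, 10.6% or 15.0%.

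**Denominators at week 12, median 1.9 months**
- On treatment: 0.365 × 20, 23, 29 = 7.3, 8.4, 10.6; pooled 0.365 × 72 = 26.3.
- With the 30-day tail: 0.524 × 20, 23, 29 = 10.5, 12.0, 15.2; pooled 37.7.

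By week 24 (168 days) the same formulas give 1/W of 5.2, 2.9 and 1.6, and 1/S of 7.5, 3.6 and 1.8. The direction is the same in every case. Only the size depends on the assumption.

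**The case against.** The strongest reply is that the protocol itself pairs this objective with type, frequency and severity of adverse events, and crude incidence by grade delivers exactly that. This stands: the endpoint is met, and the gap is against the words of the objective only.

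A reader might infer that the SAP drops a promised analysis by study day and so contradicts SAP 6.0, which declares no changes from the protocol. The documents do not support that. The phrase is qualified by where appropriate, and the same paragraph asks for adverse event incidence tables, which the SAP supplies. SAP 7.1.8 also anticipates laboratory, ECG and vital-sign statistics by nominal visit, although SAP 7.6.5 lists no such laboratory table, and performance status is tabulated by visit (SAP 7.6.10). Finally, the SAP was written against protocol Version 5, while the protocol supplied is Version 4.

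A reader might also infer that late toxicity cannot be assessed at all. That is too strong. Every onset date is listed, exposure is listed per patient, and cohorts of 20 to 29 can be reviewed case by case. For Part A, the DLT analysis is confined to Cycle 1, so one acute analysis exists. Individual review is still not a planned summary.

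Two practical objections also stand. SAP 7.1.7 presents Phase 2 by cohort, so the planned tables have no pooled column, and late cohort denominators will be small: one event in 8 patients has an exact 95% CI of 0.3% to 53%. And chronic may mean persistent rather than late, which first-onset tables alone would not capture.

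**Conclusion.** The point holds as a low-cost improvement. Within the treatment-emergent window the adverse event tables ignore time, so they do not separate early from late toxicity and they understate late-onset risk for patients who remain on treatment.

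The size is an illustration. For onset after week 12 it is about 1.9-, 1.5- and 1.2-fold across the three assumed medians when the 30-day tail counts as at risk, which is the comparison closest to the SAP's own window. It is about 2.7-, 1.9- and 1.3-fold when only patients on treatment count. Taking 2.7 alone would present a near-worst case as the estimate. All of it rests on exponential time on treatment with medians borrowed from ovarian PFS figures and applied to every cohort. The treatment past initial RECIST progression that the protocol permits would lengthen exposure and shrink the factor; early stops for toxicity would do the reverse. Deaths inside the 30-day tail are ignored.

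**What to change.** In SAP 7.6.4:
- Add tables of TEAEs and of Grade 3 or higher TEAEs by preferred term and onset interval: Cycles 1-2, Cycles 3-4, Cycle 5 onward. Give the nominal study-day equivalents (Days 1-42, 43-84, 85 onward) so that events after the last dose can be placed.
- In each interval show first-onset counts over the patients at risk at its start, defined as on treatment or within 30 days of last dose.
- Present them by cohort and pooled over Phase 2, where all patients have the same planned regimen. On-treatment cohort denominators at week 12 may be only about 7 to 11 at the shortest assumed median.
- Do the same for first Grade 3 or higher ALT, AST and CK.
- Report duration or unresolved status for Grade 3 or higher events, so that persistent toxicity is covered too.
- Flag events with imputed onset dates. Under SAP 7.1.9, a partial date that matches the treatment-start month, or gives only the treatment-start year, becomes the day after treatment start. That moves such events into the first interval.
- Name these tables as the summary of acute versus chronic toxicity.

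The cost is a few extra tables from onset dates, end dates and dosing records already collected. The downside is sparse late intervals, which the displayed denominators make plain.
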